# 9.5.9.3.5 Week 48 (End of Study)

- Perform physical examination, including measuring of weight.
- Query subjects regarding AEs and concomitant medications.
- Collect blood samples for hematology and chemistry (including glucose, CCI) analysis (see Section 9.5.7.7 for details concerning test results and study participation) and pregnancy testing for females of childbearing potential.
- Collect blood samples for ADA/NAb immunogenicity testing.
- Collect urine sample for urinalysis.
- Measure vital signs.

- •
- Enter visit data in the EDC system.

Subjects will be discharged from the study after all of the Week 48 procedures have been completed.

If a subject prematurely discontinues from the study during the Follow-up Period, he/she will be instructed to return for a clinic visit and undergo the Week 48 assessments.

[figure not shown]
## 9.6 Statistical Methods and Determination of Sample Size

### 9.6.1 Endpoints

# 9.6.1.1 Primary Endpoint

The proportion of subjects who experience a TEAE (as defined by National Cancer Institute Common Terminology Criteria for Adverse Events [NCI-CTCAE]) through Week 24 in subjects with dcSSc.

### 9.6.1.2 Efficacy Endpoints

### 9.6.1.3 Quality-of-Life Endpoints

### 9.6.1.4 Pharmacokinetic and Anti-drug Antibody Endpoints

[figure not shown]
- 1. PK of teprotumumab.
- 2. The incidence of ADA and titer levels.

# 9.6.1.5 Safety and Tolerability Endpoints

- 1. Incidence of TEAEs and AESIs (hyperglycemia, hearing impairment, infusion reaction, new onset or exacerbation of IBD).
- 2. Vital signs: change from Baseline at each scheduled visit.
- 3. Clinical safety laboratory tests: change from Baseline at each scheduled visit.

# 9.6.2 Analysis Sets

The following analysis sets will be defined for this study:

[figure not shown]
# 9.6.3 Safety, Efficacy and Quality-of-Life Endpoint Analyses

# 9.6.3.1 Primary Endpoint Analysis

The primary analysis will be conducted using the safety analysis set. The number and percentage of subjects who experience a TEAE will be summarized by treatment group.

# 9.6.3.2 Efficacy Endpoint Analyses

The efficacy analysis will be conducted using the full analysis set, with select endpoints also summarized for the per protocol analysis set.

A subject with predicted probability of at least 0.6 will be considered improved. The proportion of subjects who have improved based on column values at Week 24 will be provided with an exact 95% confidence interval around the difference in the proportion between the 2 groups (TEPEZZA minus placebo). In addition, the descriptive statistics (n, mean, standard deviation, median, maximum and minimum) of the predicted probabilities will also be provided by treatment group at each scheduled assessment visit. Descriptive summaries of the individual components of column for observed and change from Baseline will also be provided.

Using CCI data, the number and percentage of subjects with flares will be summarized by treatment group. Flare is defined as any (one or more) of the following:

- 1. Worsening of skin disease, defined by an increase of CCI by >3 units *and* new symptoms such as pruritus, redness, allodynia or new areas of skin involvement reported by the subject.
- 2. Worsening of CCl  $y \ge 0.500$  units or CCl by  $\ge 3$  (0-10 scale).
- 3. Worsening of lung function, defined as a decline in change) *and* symptoms of increased dyspnea.
- 4. New organ involvement such as CCI

Descriptive summaries for observed and change from Baseline values in IGF-1R pathway, inflammatory and fibrotic biomarkers will be summarized by treatment group at each scheduled visit.

Descriptive summaries for observed and change from Baseline values in transcriptomics associated with IGF-1R inhibition will be summarized by treatment group at each scheduled visit.

### 9.6.3.3 Quality-of-Life Analyses

Horizon Therapeutics U.S.A., Inc. Date: 02 February 2022

IND 147532

TEPEZZA (HZN-001) Protocol: HZNP-TEP-001 Version 5.0, Amendment 4

# 9.6.3.4 Safety and Tolerability Analyses

Safety analyses will be performed using the safety analysis set.

The number and percentage of subjects in each treatment group reporting at least one occurrence of a TEAE, a TEAE of grade 3 or higher, a serious TEAE, a TEAE related to study drug, an AESI and a TEAE resulting in discontinuation of treatment will be summarized by treatment group. TEAEs and SAEs will additionally be summarized by system organ class and preferred term.

Concomitant medications will be summarized by Anatomical Therapeutic Chemical Level 4 term and preferred term using counts and percentage of subjects for each treatment group.

Descriptive summaries of observed and change from Baseline values will be presented for each vital sign parameter by treatment group and visit. A shift table for weight gain and weight loss as well as hypertension by NCI-CTCAE grade and visit will be presented by treatment group.

Safety laboratory parameters (chemistry [including HbA1c], hematology, inflammatory evaluations [CCl and and urinalysis)) and change from Baseline (if applicable) will be summarized by visit and treatment group using descriptive statistics. The laboratory values will be categorized as low, normal and high based on normal ranges. Shift tables using categories of low, normal and high from Baseline to each visit will be summarized by treatment group. Additionally, a shift table for glucose by NCI-CTCAE grade and visit will be summarized by treatment group. Summaries will be provided separately for hyperglycemia.

### 9.6.4 Pharmacokinetic and Anti-drug Antibody Analyses

PK data will be analyzed using the PK analysis set. Serum concentrations of teprotumumab will be summarized descriptively, including arithmetic means, standard deviations, geometric means, coefficients of variation, medians and ranges, by time point. The relationship between clinical endpoints and the serum concentrations of teprotumumab may be explored in a descriptive manner.

Immunogenicity data will be analyzed using the safety analysis set. Immunogenicity endpoints include the incidence of ADA and NAb (of positive ADA samples) by visit and treatment group. Overall positive ADA result for a subject will be defined as at least 1 positive ADA measurement at any assayed time point. Cumulative negative result will be defined as negative ADA results at all time points for a subject.

Date: 02 February 2022

IND 147532

TEPEZZA (HZN-001) Protocol: HZNP-TEP-001 Version 5.0, Amendment 4

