- 14. Serum pregnancy test at Screening and Week 48 (or as needed). Urine pregnancy tests prior to dosing at all other visits, as applicable. Perform for female subjects of childbearing potential (including those with an onset of menopause <2 years prior to Screening, non-therapy-induced amenorrhea for <12 months prior to Screening or not surgically sterile [absence of ovaries and/or uterus]).
- 15. Vital signs (blood pressure, heart rate, respiratory rate, temperature) will be measured at all clinic visits. Vital signs will be measured pre- and post-infusion on Day 1 and Week 3 and pre-infusion on all other dosing days. Additional vital signs will be monitored if infusion-associated AEs occur (see Section 9.5.7.4 for details).
- 16. Additional ECGs will be assessed, as needed.
- 17. **CCI**
- 18. HbA1c must be ≤8.0% for randomization. If the HbA1c is elevated and considered clinically significant at any time point after Screening, it will be repeated approximately every 90 days until it returns to normal or Baseline value.
- 19. Blood samples for immunogenicity testing will be collected pre-infusion on Day 1 and Weeks 3, 12 and 18; a single sample will be collected at Weeks 24, 36 and 48. If a sample is ADA positive after confirmatory and reactive titer testing, the sample will then be tested for NAb.
- 20. AEs that occur after signing the informed consent form and prior to dosing on Day 1 will be considered Baseline signs/symptoms. AEs occurring or worsening after initiation of the infusion on Day 1 through 3 weeks (21 days) after last dose of study drug will be considered treatment-emergent AEs. AEs occurring after 3 weeks (21 days) after last dose of study drug through Week 48 will be considered follow-up AEs. All AEs and SAEs that occur from the signing of informed consent through Week 48 will be recorded.
- 21. CCI
- 22. PK samples will be collected pre- and post-infusion on Day 1 and Weeks 3, 12 and 18; a single sample will be collected at Weeks 24 and 36.
- 23. **CC**

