## 9.5.4 Immunogenicity Testing

Blood samples will be collected from all subjects for immunogenicity testing (anti-drug antibodies [ADA] and possibly neutralizing antibodies [NAb]) at the following time points: pre-infusion on Day 1 and Weeks 3, 12 and 18; a single sample will be collected at Weeks 24, 36 and 48.

If a sample is ADA positive after confirmatory and reactive titer testing, the sample will then be tested for NAb.

Instructions for collection, processing, handling, storing and shipping of immunogenicity samples will be detailed in a laboratory manual that will be provided to each site prior to site initiation.

[figure not shown]
TEPEZZA (HZN-001) Protocol: HZNP-TEP-001 Version 5.0, Amendment 4

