3. STUDY ENDPOINTS

[figure not shown]
Study endpoints are defined to address study objectives. A total of 3 subjects enrolled at the time of trial termination decision was made. Due to a small number of subjects enrolled in the study, summary statistics will be not generated for these pre-defined endpoints. Instead, by-subject listings will be provided to support an abbreviated CSR preparation.

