3.3 PK and Anti-drug Antibody Endpoints

- PK of teprotumumab.
- The incidence of anti-drug antibody (ADA) and titer levels.

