3.4 Safety and Tolerability Endpoints

Safety data such as adverse events, vital signs, and labaoratory test results will be presented in listings.

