6. LISTINGS

For the abbreviated CSR, no statistical analysis will be performed. Instead, by-subject data listings will be provided to support the CSR. Data will be presented as reported. The following listings will be provided:

- Demographics
- Inclusion/exclusion criteria
- Medical/surgical history
- Systemic sclerosis history
- Substance use
- Subject disposition
- Protocol deviation
- Safety data
- Efficacy data

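### Does counting the pre-dose Day 1 sample in the ADA-positive rule, with no ADA listing named in the SAP, leave the immunogenicity objective unreadable?

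*Protocol*

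**What the plan says.** Protocol Section 9.6.4 gives two subject-level ADA rules. The positive one reads: "Overall positive ADA result for a subject will be defined as at least 1 positive ADA measurement at any assayed time point". The negative one is its complement: "Cumulative negative result will be defined as negative ADA results at all time points for a subject". The same section also plans ADA and neutralizing antibody (NAb) incidence by visit and by arm, in the safety analysis set.

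Protocol Section 9.5.4 sets the sampling times: "pre-infusion on Day 1 and Weeks 3, 12 and 18; a single sample will be collected at Weeks 24, 36 and 48". Footnote 19 to the Schedule of Assessments agrees. Footnote 7 puts Baseline assessments before dosing, so the Day 1 sample precedes any exposure.

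The SAP was written after the sponsor ended the trial for lack of enrollment, with 3 subjects enrolled. It keeps the immunogenicity objective (Section 2.3) and the endpoint in Section 3.3: "The incidence of anti-drug antibody (ADA) and titer levels". The opening of Section 3 changes the output: "summary statistics will be not generated for these pre-defined endpoints. Instead, by-subject listings will be provided to support an abbreviated CSR preparation". Section 3.4 adds: "Safety data such as adverse events, vital signs, and labaoratory test results will be presented in listings". Section 6 says: "by-subject data listings will be provided to support the CSR. Data will be presented as reported. The following listings will be provided", and then gives nine headings: demographics, eligibility criteria, medical and surgical history, systemic sclerosis history, substance use, disposition, protocol deviations, safety data and efficacy data.

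**The concern.** Two features of the text combine. First, the positive rule does not exclude Day 1, and neither document defines treatment-induced or treatment-boosted ADA. Read literally, an antibody present before any TEPEZZA was given counts the same as one that arose afterwards. The complementary negative rule does not help, because it also includes Day 1.

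Second, the protocol's table of incidence by visit would have kept Day 1 apart, but the SAP removes all summaries. Listings are then the only output left for an objective that the SAP retains, and no heading in Section 6 mentions ADA, NAb or immunogenicity. The examples of safety data in Section 3.4 do not mention them either.

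If ADA were left out of the listings, or if the abbreviated report gave each subject only the Section 9.6.4 label, a reader could not tell a pre-existing antibody from a response to treatment.

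**Working it through.** The documents state no ADA figure to reproduce. The check is therefore mainly of the text, with some arithmetic to size the worst case.

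**Step 1. Does the rule count Day 1?** Yes. The scheduled samples are Day 1 and Weeks 3, 12, 18, 24, 36 and 48. That is seven, of which one precedes dosing.

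**Step 2. Does the current plan apply the rule?** No. SAP Sections 6 and 7 say that no statistical analysis will be performed, and Section 6 has data shown as reported. Overall positive status is a derived variable, and nothing in the SAP asks for it.

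**Step 3. Is an ADA listing promised?** In general terms, yes. The statement at the head of SAP Section 3 covers the endpoints defined in that section, and ADA incidence and titer is one of them (Section 3.3). It replaces their summaries with by-subject listings. The headings in Section 6 are broad categories; PK, also a retained endpoint in Section 3.3, has no heading of its own. The examples of safety data in Section 3.4 are introduced as examples, so the list is open. The protocol analyses immunogenicity in the safety set, which makes the safety heading its natural place.

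**Step 4. Would such a listing separate Day 1?** Yes, if it shows each result by visit. A by-subject listing of reported results in date order puts the pre-dose sample on the first line.

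**Step 5. How often could the issue arise?** Let b be the probability that a subject is ADA-positive on Day 1. The documents do not give b, so these values are assumptions. With 3 independent subjects, P(at least one positive on Day 1) = 1 − (1 − b)³.

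| b | Calculation | Result |
|---|---|---|
| 0% | 1 − 1³ | 0% |
| 1% | 1 − 0.99³ | 3.0% |
| 2% | 1 − 0.98³ | 5.9% |
| 5% | 1 − 0.95³ | 14.3% |
| 10% | 1 − 0.90³ | 27.1% |

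Mistaking a pre-existing antibody for a response to TEPEZZA also requires that the subject received TEPEZZA. The documents do not give the actual arms. Under the planned 3:2 allocation each subject has probability 0.6 of TEPEZZA, so the chance is 1 − (1 − 0.6b)³. This is 1 − 0.97³ = 8.7% at b = 5% and 1 − 0.94³ = 16.9% at b = 10%.

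**Step 6. What would the rule have done in the full trial?** Let t be the probability of a post-dose response on TEPEZZA, independent of Day 1 status. The rule gives 1 − (1 − b)(1 − t), which exceeds t by b(1 − t). At t = 0 the excess is 1, 2, 5 and 10 percentage points for b = 1, 2, 5 and 10%. At t = 20% it is 0.8, 1.6, 4 and 8 points. If placebo has post-dose positivity f and the same b, the difference between arms is [1 − (1 − b)(1 − t)] − [1 − (1 − b)(1 − f)] = (1 − b)(t − f). Day 1 positives therefore raise both arms but do not widen the contrast. The planned table by visit would also have shown them. None of this is estimated under the current SAP.

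**The case for a change.** The strongest argument for a change is that, with 3 subjects, the listing by visit is the entire immunogenicity result, so its existence should not rest on inference. Section 6 introduces its headings as the listings that will be provided, which can be read as a closed list. Table 9.2 of the protocol, the schedule of laboratory safety tests, does not include ADA, so the words about laboratory results in SAP Section 3.4 do not clearly cover it. One added line would settle the matter and needs no new data.

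Nor is a Day 1 rate of zero guaranteed. Exclusion criterion 15 bars earlier enrollment in this study or participation in an earlier teprotumumab trial, but does not expressly bar use of the marketed product, approved in January 2020. The protocol's background (Section 7.1.3.4.2) reports no clinically relevant immunogenic response in two thyroid eye disease studies and no ADA-positive treated subject in Study HZNP-TEP-302. That lends no support to the high end of the assumed range, but it comes from another disease and gives no pre-dose rate.

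What stands is that Section 6 is less specific than it could be. That does not show that ADA data will be omitted, because Section 3 already commits to by-subject listings for this endpoint. The argument about the label does not stand against this plan, since the label is not used. Treatment-induced and treatment-boosted categories are a useful convention for a study that estimates an ADA rate; this one no longer does.

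**Conclusion.** The reading of the text is correct, but no change to the plan follows. The Section 9.6.4 rule does include the pre-dose sample, yet the current SAP leaves it unused: no ADA rate, comparison or derived status is produced, so the effect on any reported figure is zero. The unnamed listing is a gap that analysts would fill sensibly from SAP Section 3, and results shown by visit already set Day 1 apart. The chance that the distinction matters for any of the 3 subjects is 0% if nobody is positive before dosing, and 3.0% to 27.1% over an assumed Day 1 rate of 1% to 10%.

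This conclusion rests on two assumptions: that the by-subject listings promised for the Section 3 endpoints include ADA, and that they show results by visit. A sponsor who wants to remove doubt could say in SAP Section 6 that ADA result, titer and NAb are listed by subject and visit with Day 1 marked as baseline. That would be optional clarification and would alter no result of the trial.

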### 9.6.5 Interim Analyses

No interim analyses are planned.

The primary analysis time point for this study is Week 24. Therefore, the database will be locked after all subjects complete Week 24 assessments or withdraw from study prematurely prior to Week 24 for primary analyses. Select Sponsor personnel/designees may be unblinded after the database lock for the Week 24 analyses.

# 9.6.6 Multiple Comparisons

While p-values will be calculated for many endpoints, decision-making will not be based on formal testing procedures. Nominal p-values, whether or not they are less than 0.05, will be considered in conjunction with estimates of magnitude of treatment effect and consistency of direction in planning future studies. As such, no adjustment for multiple comparisons will be made.

# 9.6.7 Sample Size and Power Considerations

For a TEAE that occurs in 20% of TEPEZZA-treated subjects in the dcSSc population, a sample size of 15 subjects provides approximately 95% probability that the TEAE will be observed at least once.

This study is not powered to detect a statistically significant difference in the proportion of responders unless the difference is very large. For example, if 10% of all placebo subjects were responders and 75% of all TEPEZZA subjects were responders, this study would have 87% power to detect that difference ( $\alpha$ =0.05, 2-tailed).

# 9.7 Changes in the Conduct of the Study

If any modifications in the experimental design, dosages, parameters, subject selection or any other sections of the protocol are indicated or required, the Investigator will consult with the Sponsor before any such changes are instituted. Modifications will be accomplished through formal amendments to this protocol by the Sponsor and approved from the appropriate IRB/IEC.

The Sponsor's Medical Monitor will consider any requests for exceptions to protocol entry criteria on a case-by-case basis. The Investigator or other health professional in attendance must contact the Sponsor as soon as possible. All protocol deviations and the reasons for such deviations **must** be documented into the electronic database. In the event of a protocol deviation, the Investigator and Sponsor's Medical Monitor will determine whether the subject should continue to participate in the study.

The Sponsor has a legal responsibility to report fully to regulatory authorities all results of administration of investigational drugs to humans. No investigational procedures other than those described in this protocol will be undertaken on the enrolled subjects without the agreement of the IRB/IEC and Sponsor.

TEPEZZA (HZN-001) Protocol: HZNP-TEP-001 Version 5.0, Amendment 4

#### 10 SOURCE DOCUMENTATION AND INVESTIGATOR FILES

The Investigator must maintain adequate and accurate records to document fully the conduct of the study and to ensure that study data can be subsequently verified. These documents should be classified in 2 separate categories: (1) Investigator study file and (2) subject clinical source documents that corroborate data collected in the eCRFs. Subject clinical source documents would include, as applicable, original hospital/clinic subject records; physicians' and nurses' notes; appointment book; original laboratory, ECG, electroencephalogram, radiology, pathology and special assessment reports; dispensing records; signed ICFs; consultant letters; and subject Screening and enrollment logs.

In order to comply with regulatory requirements, it is the policy of the Sponsor that, at a minimum, the following be documented in source documents at the study center:

- Medical history/physical condition and diagnosis of the subject before involvement in the study sufficient to verify that the subject meets protocol entry criteria.
- Study number, assigned subject number and verification that written informed consent was obtained (each recorded in dated and signed progress notes).
- Progress notes for each subject visit (each dated and signed).
- Records of each study visit including each study assessment and the identity of the staff member performing the assessment.
- Study drug dispensing and return.
- Review by the Investigator or qualified personnel on the 1572 of laboratory test results.
- AEs (start and stop date, description, action taken and resolution).
- Investigator or Sub-Investigator's signed assessment of each AE.
- Concomitant medications (start and stop dates, reason for use).
- Condition of subject upon completion of, or premature withdrawal from, the study.

Date: 02 February 2022

IND 147532

TEPEZZA (HZN-001) Protocol: HZNP-TEP-001 Version 5.0, Amendment 4

# 11 CASE REPORT FORMS

An eCRF is required for every subject who signs the ICF. Required data must be entered on the eCRF within the required time period, which will be outlined within each site agreement, after data collection or the availability of test results. Separate source records are required to support all eCRF entries.

The Investigator will ensure that the eCRFs are accurate, complete, legible and timely and will review and provide an electronic signature for the eCRF according to the standard operating procedure of the Data Management System. Final eCRFs will be provided to the Investigator and Sponsor by Data Management.

### 12 STUDY MONITORING

The Investigator will ensure that the study is conducted in accordance with all regulations governing the protection of human subjects. The Investigator will adhere to the basic principles of GCP as outlined in Title 21 of the CFR, Part 312, Subpart D, "Responsibilities of Sponsors and Investigators"; 21 CFR, Part 50, "Protection of Human Subjects"; 21 CFR, Part 56, "Institutional Review Boards"; 21 CFR, Part 54 "Financial Disclosure by Clinical Investigators"; and the ICH guideline entitled "Good Clinical Practice: Consolidated Guidance." Additionally, this study will be conducted in compliance with the Declaration of Helsinki and with all local laws and regulations.

The Investigator will ensure that all work and services described in, or associated with, this protocol are conducted in accordance with the investigational plan, applicable regulations and the highest standards of medical and clinical research practice. The Investigator will provide copies of the study protocol and Investigator's Brochure to all Sub-Investigators, pharmacists and other staff responsible for study conduct.

All aspects of the study will be monitored by qualified individuals designated by the Sponsor. The Sponsor will ensure that the study is monitored adequately in accordance with GCP guidelines.

Prior to initiation of the study, the Sponsor's representatives will review with study center personnel information regarding the investigational drug, protocol requirements, monitoring requirements and reporting of SAEs.

At intervals during the study, as well as after the completion of subject enrollment, the study center will be monitored by the Sponsor or designee for compliance. During these visits, the blinded monitor will discuss study progress, verify adherence to the protocol and verify the completeness, consistency and accuracy of the data being entered on the eCRF (source data verification); oversee the resolution of outstanding data discrepancies; and check on various aspects of study conduct (e.g., sample storage). The Investigator agrees to allow unblinded monitors access to the clinical supplies, dispensing and storage areas and clinical records of the study subjects and, if requested, agrees to assist the monitors. The Investigator must cooperate

Date: 02 February 2022

IND 147532 Version 5.0, Amendment 4
with the monitors to ensure that any problems detected in the course of these monitoring visits

with the monitors to ensure that any problems detected in the course of these monitoring visits are resolved.

A secondary audit may be conducted by Quality Assurance designated by the Sponsor. The Investigator will be informed if this is to take place and advised as to the nature of the audit. Representatives of the US FDA and/or representatives of other regulatory authorities may also conduct an inspection of the study at the investigative site. If informed of such an inspection, the Investigator should notify the Sponsor immediately.

Every effort will be made to maintain the anonymity and confidentiality of subjects participating in this clinical study. However, because of the investigational nature of this treatment, the Investigator agrees to allow representatives of the Sponsor, its designated agents and authorized employees of the appropriate regulatory agencies to inspect the facilities used in this study and to have direct access to inspect, for purposes of verification, the hospital or clinical records of all subjects enrolled in this study. A statement to this effect should be included in the ICF.

